2.1 Interim Analysis

No interim analysis is planned.

2.2 Final Analyses

The final planned primary analyses will be performed after the completion of the following sequential steps:

1. All subjects have completed the study as defined in the protocol.
2. All required database cleaning activities have been completed and database has been locked.
3. All criteria for unblinding the randomization codes have been met and the randomization codes have been distributed.

3 Considerations for Data Analyses and Data Handling Conventions

3.1 Baseline Definition

For all endpoints the baseline value will be the latest pre-dose assessment with a non-missing value.

3.2 Subgroups/Stratifications

Subjects will be stratified by their baseline total MLSI (A×I) score for the facial surfaces of 4 of the 12 anterior teeth (<15 (low); ≥15 (high)), and depending on which strata they fall under

| | | | | |
|---|------------------|--|---------------------|----------------|
|  GlaxoSmithKline | Document Name | gsk-208078-reporting-and-analysis-plan.pdf | | |
| | Type | Version | Document Identifier | Effective Date |
| | elido_controlled | 0.1, CURRENT; Most-Recent; In Review | 090032d580f4eeeb | |
| | Reason For Issue | | | |

Potassium Nitrate / Sodium Fluoride

208078

Final Statistical Reporting and Analysis plan Amendment 21NOV2017

will be assigned their allocated test product from either the “low” or “high” randomization schedule. The strata will be identified as:

Strata 1: Low (MLSI <15)

Strata 2: High (MLSI \geq 15)

Efficacy variables will be analysed accounting for strata. Subgroups are not defined for this trial.

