4.4 Analysis of Efficacy

4.4.1 Primary Efficacy Endpoint

4.4.1.1 Primary Efficacy Endpoint Definition

The primary efficacy variable is the change from baseline in overall MLSI score. The primary time-point is 8 weeks. The overall MLSI (A×I) for each subject is derived at a tooth site level first before averaging over all the non-missing teeth sites assessed. The change from baseline is derived from the individual sites first before calculating the average change across the sites assessed.

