4.4.1.2 Statistical Hypothesis, Model, and Method of Analysis

The primary objective is to evaluate the ranking order in extrinsic dental stain removal, as measured by overall MLSI (A×I), of a 0.5% spherical silica dentifrice, a marketed 6% abrasive silica dentifrice, a 1% spherical silica / 5% STP dentifrice, and a marketed 16% abrasive silica / 5% STP dentifrice, after 8 weeks twice daily brushing.

Summary statistics including mean, SD, median, min, max will be provided for baseline and Week 8 by randomized treatment group ([Table 14.2.2.1](#)). The change from baseline in overall MLSI will be analyzed using analysis of covariance (ANCOVA) with treatment as a fixed effect and baseline overall MLSI as a covariate.

| | | | | |
|---|------------------|--|---------------------|----------------|
|  GlaxoSmithKline | Document Name | gsk-208078-reporting-and-analysis-plan.pdf | | |
| | Type | Version | Document Identifier | Effective Date |
| | elido_controlled | 0.1, CURRENT; Most-Recent; In Review | 090032d580f4eeeb | |
| | Reason For Issue | | | |

Potassium Nitrate / Sodium Fluoride

208078

Final Statistical Reporting and Analysis plan Amendment 21NOV2017

There are no comparisons for the primary objective as the main objective is to look at the rank order of the treatments in level of stain reduction after 8 weeks of treatment. This will be achieved via the adjusted means and confidence intervals (Cis) for the means along with plots of MLSI over time. Adjusted means of all treatments will be provided together with their 95% Cis and p-values ([Table 14.2.2.2](#)).

The assumption of normality and homogeneity of variance in the ANCOVA model will be investigated. Violation of this assumption will be overcome using a suitable data transformation or a non-parametric technique (e.g. Wilcoxon Rank Sum test).

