4.5 Analysis of Secondary Objectives

4.5.1 Efficacy

The hypothesis is that the test products will reduce stain to a similar or greater extent than the reference products.

Two comparisons of interest will be done under the secondary objectives. These comparisons are:-

Test Product 1 vs Reference Product 1

Test Product 2 vs Reference Product 2.

The change from baseline in overall MLSI at Week 8 will be analyzed using ANCOVA with treatment as a fixed effect and baseline overall MLSI as a covariate.

From the above ANCOVA model, treatment differences between groups (Test Product 1 vs Reference Product 1 and Test Product 2 vs Reference Product 2), 95% Cis and p-values, will be provided ([Table 14.2.2.2](#)).

The assumption of normality and homogeneity of variance in the ANCOVA model will be investigated. Violation of this assumption will be overcome using a suitable data transformation or a non-parametric technique (e.g. Wilcoxon Rank Sum test).

| | | | | |
|---|------------------|--|---------------------|----------------|
|  GlaxoSmithKline | Document Name | gsk-208078-reporting-and-analysis-plan.pdf | | |
| | Type | Version | Document Identifier | Effective Date |
| | elido_controlled | 0.1, CURRENT; Most-Recent; In Review | 090032d580f4eeeb | |
| | Reason For Issue | | | |

Potassium Nitrate / Sodium Fluoride

208078

Final Statistical Reporting and Analysis plan Amendment 21NOV2017

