4.6.1.2 Analysis of Exploratory Variables

Summary statistics including mean, SD, median, min, and max will be provided for week 2 and week 4 by randomized treatment group ([Table 14.2.2.1](#)).

All stain variables will be analyzed as per the primary efficacy variable using the appropriate baseline values as a covariate.

The change from baseline in TPI variables will be analyzed using analysis of covariance (ANCOVA) with treatment and MLSI stratification as fixed effects and appropriate baseline (pre-treatment) TPI as a covariate.

From ANCOVA model, the adjusted mean for each treatment group will be provided with 95% Cis and corresponding p-values.

Results for overall interproximal MLSI (AxI) score, overall MLSI area score, overall MLSI intensity score, overall TPI score and overall Interproximal TPI Score will be presented in [Table 14.2.3.1](#), [Table 14.2.3.2](#), [Table 14.2.4.1](#), [Table 14.2.4.2](#), [Table 14.2.5.1](#), [Table 14.2.5.2](#), [Table 14.2.6.1](#), [Table 14.2.6.2](#) and [Table 14.2.7.1](#), [Table 14.2.7.2](#) respectively.

| | | | | |
|---|------------------|--|---------------------|----------------|
|  GlaxoSmithKline | Document Name | gsk-208078-reporting-and-analysis-plan.pdf | | |
| | Type | Version | Document Identifier | Effective Date |
| | elido_controlled | 0.1, CURRENT; Most-Recent; In Review | 090032d580f4eeeb | |
| | Reason For Issue | | | |

Potassium Nitrate / Sodium Fluoride

208078

Final Statistical Reporting and Analysis plan Amendment 21NOV2017

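### The SAP says efficacy variables are analysed accounting for strata, but the stain models have no stratum term and the only rank fallback named uses neither stratum nor baseline

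*SAP*

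**What the plan says.** - **General rule.** SAP Amendment 3.2 defines two strata by baseline total MLSI (A×I) on four anterior teeth, cut at 15, and states "Efficacy variables will be analysed accounting for strata". It makes no exception.
- **Primary stain model (4.4.1.2).** "analysis of covariance (ANCOVA) with treatment as a fixed effect and baseline overall MLSI as a covariate". The Table 14.2.2.2 footnote lists the same two terms.
- **Secondary comparisons (4.5.1).** Test Product 1 vs Reference Product 1 and Test Product 2 vs Reference Product 2 at Week 8; the outcome "will be analyzed using ANCOVA with treatment as a fixed effect and baseline overall MLSI as a covariate".
- **Exploratory stain variables (4.6.1.2).** "All stain variables will be analyzed as per the primary efficacy variable using the appropriate baseline values as a covariate".
- **Plaque (4.6.1.2).** The TPI model is the only one that carries the stratum: "with treatment and MLSI stratification as fixed effects and appropriate baseline" TPI as covariate.
- **Fallback if assumptions fail (4.4.1.2, repeated in 4.5.1).** "a suitable data transformation or a non-parametric technique (e.g. Wilcoxon Rank Sum test"). Protocol 10.2.2 gives two examples at this point, Wilcoxon and Van Elteren. The original SAP and the Amendment keep only the first.
- **Ranking.** The four-arm ranking rests on ANCOVA output: "Adjusted means of all treatments will be provided together with their 95% Cis and p-values".

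**The concern.** Randomisation is stratified on baseline stain, and 3.2 promises that the efficacy analyses reflect this. Read literally, the stain models do not. A programmer cannot tell whether 3.2 calls for a stratum term or whether the baseline covariate is meant to satisfy it.

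The two parts of the stain analysis need separate treatment. An ANCOVA on baseline MLSI already adjusts for the quantity that defines the strata. A Wilcoxon rank sum test on change scores adjusts for nothing. If baseline predicts change, stratified randomisation has removed part of the between-arm variability, but the unstratified test still counts it as noise. The test is then too cautious. What is at stake is power for the two secondary comparisons, and only if the fallback is used.

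**Working it through.** **1. Does the ANCOVA covariate carry the stratum?** Protocol 7.1.1 divides each facial surface into four regions, so 4 teeth × 4 regions = 16 sites. SAP 4.4.1.1 derives A×I at each site "before averaging over all the non-missing teeth sites assessed". With all 16 sites scored, overall MLSI = total/16, and the cut of 15 becomes 15/16 = 0.94 on the covariate's scale. The stratum is then a dichotomy of the covariate. For the interproximal, area and intensity scores the covariate is a different baseline, so the link is incomplete.

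**2. Assumptions.** The documents do not disclose SDs, correlations or a target effect, so there is no plan figure to reproduce. The simulation used:
- 120 subjects in four arms, blocks of 8 within stratum (sample size from SAP 1.1, block size from the Listing 16.1.7 footnote);
- assumed baseline total = round(15·exp(0.35z)), z standard normal, which puts 54% in the high stratum;
- assumed baseline to Week 8 correlation ρ from 0.3 to 0.85, and Week 8 SD equal to k times baseline SD, k = 1 or 0.75;
- assumed residuals of the kind that would trigger the fallback: t(3), lognormal skew, or variance rising with baseline;
- effect 0.735 residual SD, chosen for about 80% ANCOVA power: 0.735 × √(30/2) = 2.85; 2.85 − 1.98 = 0.87; Φ(0.87) = 0.81;
- 4,000 runs per cell (Monte Carlo SE about 0.2 to 0.35 points under the null, up to 0.8 for power).

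**3. Hand check of the direction.** The correlation of change with baseline is r = (kρ − 1)/√(1 + k² − 2kρ). A median split of a normal baseline keeps 2/π = 0.637 of r² as between-stratum variance. Stratified randomisation balances that share, so the Wilcoxon null error is roughly 2Φ(−1.96/√(1 − 0.637r²)). For k = 1, ρ = 0.3: r = −0.7/√1.4 = −0.59; 0.637 × 0.35 = 0.223; 1.96/√0.777 = 2.22; error about 2.6%.

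**4. Results** (ranges over the three residual shapes; gain is Van Elteren minus Wilcoxon power, in points)

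| k | ρ | r | Hand check | Wilcoxon error % | Van Elteren error % | Gain |
|---|---|---|---|---|---|---|
| 1 | 0.3 | −0.59 | 2.6 | 1.2–2.1 | 4.7–5.3 | 6.6–10.5 |
| 1 | 0.5 | −0.50 | 3.3 | 2.4–3.0 | 4.7–5.3 | 4.5–6.0 |
| 1 | 0.7 | −0.39 | 3.9 | 3.3–3.8 | 5.1–5.5 | 2.4–2.7 |
| 1 | 0.85 | −0.27 | 4.5 | 3.6–4.3 | 4.3–5.3 | 0.9–2.5 |
| 0.75 | 0.3 | −0.73 | 1.6 | 0.9–1.2 | 4.8–5.1 | 17.7–22.5 |
| 0.75 | 0.5 | −0.69 | 1.9 | 1.0–1.5 | 4.6–4.9 | 11.8–19.3 |
| 0.75 | 0.7 | −0.66 | 2.1 | 1.3–1.8 | 4.6–4.9 | 11.1–17.3 |
| 0.75 | 0.85 | −0.68 | 2.0 | 1.4–1.5 | 4.3–5.2 | 11.9–18.0 |

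- Uneven strata (25% or 80% high; ρ = 0.5, k = 1): Wilcoxon error 2.8–3.5%, gain 3.6–5.9 points.
- Baseline unrelated to change: Wilcoxon error 5.0–5.6%, gain −0.1 to 2.0 points.

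**5. ANCOVA.** For overall MLSI, type I error is 3.9–5.9% without the stratum and 4.0–5.9% with it; adding it changes power by −0.5 to +0.6 points. For sub-scores assumed to correlate 0.86 to 0.95 with the total, the stratum removes 0.1–9.9% of residual variance, which would lift 80% power to between 80.0% and 84.0%.

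**The case against.** The best defence is that the plan is coherent in substance. The protocol leaves the stratum out of the stain model and adds it for TPI, whose baseline does not measure stain; the SAP follows both. For overall MLSI, adjusting for baseline does account for strata. That stands, so a reader who infers that the primary ANCOVA ignores the stratified randomisation would be wrong.

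A second tempting inference is that the SAP dropped a protocol-specified test without recording it. The documents do not support that. Both lists are examples, the protocol itself offers Wilcoxon, and Van Elteren is not excluded. The absence of a row in SAP Section 5 is minor.

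Third, the harm needs several things together: assumptions judged violated, a rank test preferred to a transformation, the unstratified version chosen, and baseline predicting change. Protocol 1.2.2 might be read as expecting the last of these, but it explains why stained teeth are selected and does not say that a subject's baseline predicts change. Nor is there a general loss against ANCOVA: at k = 1 Wilcoxon power was 77–97% (ANCOVA 80–84%), though at k = 0.75 it was 57–81% (ANCOVA 81–83%).

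Finally, prescribing Van Elteren alone would exclude a rank ANCOVA on baseline. In a check at 1,500 runs per cell, a Quade-type version held 4.1–6.1% type I error. Its power was about 3 to 11 points above Van Elteren at k = 0.75 and about −2 to +5 at k = 1. This stands and shapes the fix.

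What remains is that 3.2 and the stain sections do not agree as written, and that the one rank test named does not do what 3.2 promises.

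**Conclusion.** The concern holds in a limited form. For the overall MLSI ANCOVA, primary and secondary, it is a matter of wording. For the exploratory sub-scores the covariate carries the stratum less completely, with a small effect.

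The material part is the fallback for the two secondary comparisons. If it is used and baseline predicts change, the unstratified Wilcoxon test runs at about 1 to 4% type I error. It gives up about 1 to 11 points of power at equal SDs, and about 11 to 23 points if the Week 8 SD is three quarters of the baseline SD. The loss is near zero if baseline does not predict change. These sizes rest on assumed correlations, SD ratios and residual shapes; the direction follows from stratified randomisation.

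A reader might also infer a false-positive risk or a threat to the primary ranking. Neither follows: the error is on the conservative side, and the ranking uses the ANCOVA adjusted means, as SAP 4.4.1.2 and Addendum 1 Section 5 say. The change is worth making because it costs little, but this is a proof-of-principle study with no comparison attached to its primary objective.

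**What to change.** 1. **SAP 4.4.1.2 and 4.5.1.** Replace the Wilcoxon example with a rank method that respects the stratification: the Van Elteren test by MLSI stratum, which the protocol already names, or a rank ANCOVA on baseline. State that it applies to Test Product 1 vs Reference Product 1 and Test Product 2 vs Reference Product 2. Name one of the two.
2. **SAP 3.2.** Either state that stain ANCOVAs account for strata through the baseline stain score, or add MLSI stratum as a fixed effect in 4.4.1.2, 4.5.1, 4.6.1.2 and the Table 14.2.2.2 footnote.
3. **Timing.** Addendum 1 says its changes arose after unblinding. Label any change made now as post hoc and add a row for it in Section 5.

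**Cost.** Wording only; no new data. Van Elteren gives no adjusted difference or confidence interval, so those columns of Table 14.2.2.2 stay on the ANCOVA. Adding the stratum term uses 1 of 120 − 5 = 115 residual degrees of freedom, with a variance inflation factor of about 2.3 against baseline MLSI under the assumed distribution. The fix does not settle when assumptions count as violated, or when a transformation is preferred to a rank test.

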3.3 Timepoints and Visit Windows

Time windows for this study are as the following:

- Visit 2 (MLSI Baseline) is minimum 24 hours and maximum two weeks from Visit 1 (Screening)
- Visit 3 (TPI Baseline) is 24 hours after Visit 2
- Visit 4 (Week 2) is 14 ± 1 days from Visit 2.
- Visit 5 (Week 4) is 28 ± 2 days from Visit 2.
- Visit 6 (Week 8) is 56 ± 3 days from Visit 2.
- Visit 7 (Week 8) is 57 ± 3 days from Visit 2.

All data will be accepted for the analysis. Deviations from the scheduled visit window are considered to be minor.

4 Data Analysis

Data analysis will be performed by inVentiv Health Clinical. The statistical analysis software used will be SAS version 9.4 (Studio).

Prior to database closure a BDRM will be conducted in which various aspects of the trial will be discussed and agreed.

Unless otherwise described below, all listings will be produced for all randomized subjects.

4.1 Populations for Analysis

Tables described in this section other than disposition will be produced for all randomized subjects.

4.1.1 Subject Disposition

Screen failures are defined as subjects who consent to participate in the clinical study but are not subsequently randomized. A summary will be provided of the number of subjects screened and the number of screen failures with reasons why subjects were not randomized.

GlaxoSmithKline Consumer Healthcare Confidential

Page 10 of 53

| | | | |
|------------------|--|---------------------|----------------|
| Document Name | gsk-208078-reporting-and-analysis-plan.pdf | | |
| Type | Version | Document Identifier | Effective Date |
| elido_controlled | 0.1, CURRENT; Most-Recent; In Review | 090032d580f4eeeb | |
| Reason For Issue | | | |

Potassium Nitrate / Sodium Fluoride

208078

Final Statistical Reporting and Analysis plan Amendment 21NOV2017

Subject disposition will be summarized as the number and percentage of subjects (out of the number of randomized subjects) who complete the study, with the number who discontinue broken down by reason for discontinuation ([Table 14.1.1](#)). The table will also summarize the number and percent of subjects assigned to each analysis population (refer to section 4.1.3).

Subject disposition including the subject status (completer, Yes/No), critical demographic data (age, sex, race, ethnicity), the duration of treatment before discontinuation and the specific reason for discontinuation, will be listed in for randomized subjects ([Listing 16.2.1.1.1](#)) by treatment group and in for non-randomized subjects ([Listing 16.2.1.1.2](#)).

4.1.2 Protocol Deviations

Important protocol deviations (including deviations related to study inclusion/exclusion criteria, conduct of the trial, patient management or patient assessment) will be listed.

Protocol deviations will be tracked by the study team throughout the conduct of the study. Data will be reviewed prior to unblinding and hard lock of the database to ensure all important deviations are captured and categorised.

Violations that influence the efficacy outcome will be given in the “Review Listing Requirement (RLR)” document and important violations will be identified in blinded data review stage.

The number and percentage of subjects with any important protocol deviations and with each type of major protocol deviations will be presented by treatment ([Table 14.1.2](#)). All protocol deviations will be listed ([Listing 16.2.2](#)).

4.1.3 Analysis Populations

Five analysis populations are defined.

| Population | Definition / Criteria | Analyses Evaluated |
|-----------------------|--|---|
| All Screened Subjects | 
 All subjects who enter the study and sign the informed consent form. This population includes screen failures as well as those that are randomized. | 
 Disposition, AE listing |
| Randomized | 
 All subjects who are randomized and may or may not receive the application of the study products. Any subject who receives a treatment randomization number will be considered to have been randomized. | 
 Protocol violations |
| Safety | 
 Comprise of all subjects who are randomized and receive at least one dose of study treatment. | 
 Safety Analysis |

GlaxoSmithKline Consumer Healthcare Confidential

Page 11 of 53

| | | | |
|------------------|--|---------------------|----------------|
| Document Name | gsk-208078-reporting-and-analysis-plan.pdf | | |
| Type | Version | Document Identifier | Effective Date |
| elido_controlled | 0.1, CURRENT; Most-Recent; In Review | 090032d580f4eeeb | |
| Reason For Issue | | | |

Potassium Nitrate / Sodium Fluoride

208078

Final Statistical Reporting and Analysis plan Amendment 21NOV2017

| Population | Definition / Criteria | Analyses Evaluated |
|-----------------|---|--|
| | 
 This population will be based on the treatment the subject actually received. | |
| Intent-To-Treat | 
 Comprises of all randomized subjects who receive the study treatment at least once and provide at least one post-baseline (post treatment) assessment of efficacy. This population will be based on the treatment to which the subject was randomized. | 
 Efficacy |
| Repeatability | 
 Any subject who has a repeat stain or plaque assessment. The repeat stain and plaque populations will be separate populations. MLSI repeatability population and TPI repeatability population will be subset of the repeatability population. | 
 Repeatability Analysis |

The numbers of subjects included in each of the analysis populations, and the number excluded from each population (except repeatability population) broken down by the reason for exclusion will be presented ([Table 14.1.3](#)). Subjects excluded from any of the analysis populations will be listed ([Listing 16.2.3.1](#)), with the reason for exclusion.

4.2 Subject Demographics and Other Baseline Characteristics

Demographic and baseline characteristics summaries will be produced for the ITT and Safety populations by treatment group.

4.2.1 Demographic Characteristics

Categorical demographic variables include sex, race, strata and ethnicity. These variables will be summarized by the number and percentage of subjects with each relevant characteristic in each treatment group. Age will be summarized by the mean, standard deviation (SD), median (med), minimum (min) and maximum (max) values in each treatment group. All demographic information will be tabulated in [Table 14.1.4.1](#) for the Safety population, [Table 14.1.4.2](#) for the ITT population and listed in [Listing 16.2.4.1](#).

| | | | | |
|---|------------------|--|---------------------|----------------|
|  GlaxoSmithKline | Document Name | gsk-208078-reporting-and-analysis-plan.pdf | | |
| | Type | Version | Document Identifier | Effective Date |
| | elido_controlled | 0.1, CURRENT; Most-Recent; In Review | 090032d580f4eeeb | |
| | Reason For Issue | | | |

Potassium Nitrate / Sodium Fluoride

208078

Final Statistical Reporting and Analysis plan Amendment 21NOV2017

4.2.2 General Medical History

Medical diagnoses/surgeries will be listed in [Listing 16.2.4.2](#), with start date and end date or ongoing at the start of study drug.

4.3 Study Product Compliance and Use of Other Therapy

4.3.1 Study Product Compliance

Brushing compliance (using study products twice daily) will be listed ([Listing 16.2.5.1](#)). This listing will include expected number of brushing, actual number of brushing and percentage of compliance.

4.3.2 Prior and Concomitant Medication

Prior medications will be listed by subject, with, indication, dose, dose form, frequency, route, start date and end date ([Listing 16.2.5.5](#)). Prior medications are defined as those stopped before the first administration of the study products. Concomitant medications will be listed similarly ([Listing 16.2.5.6](#)). Concomitant medications are defined as those ongoing or started on or after the first administration of the study products.

